#### Calcium and Phosphate Regulation

Serum calcium and phosphate levels are regulated principally by parathyroid hormone (PTH), the active vitamin D metabolite 1,25-dihydroxyvitamin D (1,25[OH]2 vitamin D; calcitriol), and calcitonin. PTH maintains an inverse relationship with serum calcium. Normal total serum calcium levels (generally 8.4 to 10.2 mg/dL) and serum phosphate levels (2.5 to 4.5 mg/dL) are regulated to yield a calcium phosphate product of approximately 35 mg/dL. This product is important because of the potential for calcium phosphate salts to be deposited in soft tissues. Levels of the calcium phosphate product that exceed 50 mg/dL are believed to place patients at risk for ectopic soft tissue calcification. PTH is synthesized and secreted by the parathyroid glands primarily in response to a fall in serum calcium levels. Through concerted actions on the kidney and bone, PTH is the principal regulator of plasma calcium homeostasis. In the kidney,

PTH increases renal tubular reabsorption of calcium (while inversely inhibiting phosphate reabsorption) and increases the synthesis of 1,25(OH)2 vitamin D from its precursor 25-hydroxyvitamin D (25[OH] vitamin D). Although 1,25(OH)2 vitamin D has a short in vivo half-life (approximately 6 hours), it directly increases intestinal calcium and phosphate absorption. In bone, PTH increases the efflux of calcium from bone, both from the rapidly exchangeable pool of calcium within bone, and by increasing the number and activity of osteoblasts and osteoclasts, thereby increasing bone turnover. As PTH also acts to inhibit the reabsorption of phosphate in the proximal nephron, it prevents an increase in plasma phosphate levels that could result from increased intestinal phosphate absorption and efflux of phosphate from bone. Calcitonin, secreted by C-cells of the thyroid gland, decreases serum calcium by inhibiting bone resorption and promoting renal tubular calcium excretion, but its effects are relatively minor in comparison to those of PTH and 1,25(OH)2 vitamin D ([Bilezikian et al. 2001](#)).

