### 3 STUDY DESIGN

#### 3.1 Overall Design and Control Methods

This study is a long-term, open-label study using rhPTH[1-84] for the treatment of adult male and female subjects with hypoparathyroidism. The subjects must have previously completed the NPSP558 RELAY study (8 weeks of active therapy) and/or previously completed the NPSP558 REPLACE study (CL1-11-040) (Visit 18).

The goal of this study is to optimize rhPTH[1-84] dosing while reducing calcitriol and oral calcium (carbonate or citrate) supplementation to as low as safely possible while maintaining total serum calcium levels (see [Appendix 2](#), rhPTH[1-84] and Supplement Titration Guideline).

- The starting dose of rhPTH[1-84] for this study will be 25 or 50 µg SC once daily (QD).
- Subjects with a total serum calcium value of  $\leq 9.5$  mg/dL will have a starting dose of 50 µg.
- Subjects with a total serum calcium value of  $> 9.5$  mg/dL will have a starting dose as follows:
  - Subjects who are taking supplements ( $\geq 500$  mg calcium and/or any calcitriol) will have the supplements reduced or stopped and will start at a dose of 50 µg SC QD.
  - Subjects who are taking minimal or no supplemental calcium ( $< 500$  mg) and no calcitriol will have a starting dose of 25 µg SC QD.
- Study visits during the first 12 months of the study will be conducted at Weeks 1 (baseline), 4, 8, and then every 8 weeks thereafter up to Week 48 (Visit 8). The Week 52 visit (Visit 9) is scheduled 4 weeks later.
- At the end of Week 52, subjects will be invited to extend their study drug regimen until January 2018 or after the completion of the last patient's Month 72 visit, whichever comes last. During this time, subjects will return to the clinic for interim visits every 2 months (Months 14, 16, 18, etc).
- All subjects will have their total serum calcium checked by a local laboratory 3 to 5 days ( $\pm 2$  days) following the baseline visit.
- Subjects may have their rhPTH[1-84] dose increased in increments of 25 µg to a maximum of 100 µg SC QD by the investigator at any time during the study, with the goal of achieving or maintaining total serum calcium levels in the range of 8.0 to 9.0 mg/dL. The rhPTH[1-84] dose may be adjusted downward at any time as needed to maintain appropriate serum calcium levels (approximately 8.0 to 9.0 mg/dL) or due to any safety concerns.

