- Adjustment of supplemental calcium and calcitriol regimens will be based on serum calcium levels, with the goal to be a reduction or removal of calcitriol treatment to the maximum degree clinically possible and to decrease the prescribed oral calcium supplementation to  $\leq 500$  mg daily.
- Subjects will have blood draws to assess total serum calcium levels (which may be performed locally) 3 to 5 days after ANY dose adjustment of rhPTH[1-84], after any significant change in doses of calcium and/or and calcitriol supplements, or at any other time

at the discretion of the investigator. Results of local total serum calcium levels will be recorded in the source document.

[figure not shown]
- Once a subject achieves a stable serum calcium (target: between 8.0 and 9.0 mg/dL) with the minimum doses of supplements possible, they will be maintained at that dose of rhPTH[1-84].
- If ANY predose (trough) total serum calcium is > 11.9 mg/dL study drug will be stopped. Once total serum calcium returns to the normal range, rhPTH[1-84] can be reintroduced. The rhPTH[1-84] dose may be maintained at the previous level if reductions in oral calcium supplements and/or calcitriol are possible. If oral calcium supplements have been previously reduced to ≤ 500 mg daily and calcitriol has been eliminated, then rhPTH[1-84] should be reintroduced at the next lowest dose level and supplemental oral calcium and calcitriol should then be adjusted accordingly to obtain a predose total serum calcium level of approximately 8.0 to 9.0 mg/dL.
- If the predose total serum calcium level remains above 10.0 mg/dL for two or more safety assessments or study visits on normal dietary intake and study drug alone, then the rhPTH[1-84] dose may be reduced to the next lowest dose level and supplemental oral calcium and calcitriol then adjusted accordingly to obtain a predose total serum calcium level of approximately 8.0 to 9.0 mg/dL. Study medication will be stopped if the predose total serum calcium remains above the upper limit of the laboratory normal range (ULN) for two or more safety assessments or study visits (no more than 5 days apart) at the lowest dose regimen, following withdrawal of all supplementary oral calcium and calcitriol therapy. Further choices on adaptation of treatment regimens, reinstitution of previous therapy, or discontinuation from study will be made in consultation with the Shire medical monitor.

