## Hypocalcemia

If the total serum calcium level falls below 8.0 mg/dL (or below the baseline values, if the subject entered the study with a total serum calcium < 8.0 mg/dL), then the subject's calcitriol and oral calcium doses should be checked and the injection technique of rhPTH[1-84] reviewed with the subject to ensure proper administration. At planned study visits (Week 4, 8 etc) the rhPTH[1-84] dose can be uptitrated if indicated in the opinion of the investigator following discussion with the sponsor. During interim safety checks, hypocalcemia should be addressed by clinically indicated increases in calcitriol or supplemental oral calcium doses according to the guideline below, with the goal of attaining a total serum calcium level of 8.0 to 9.0 mg/dL. Laboratory testing should be repeated as indicated in order to ensure that changes in dosing are accompanied by improved serum calcium levels.

Visit number	Serum calcium (mg/dL)	rhPTH[1-84] dose	Supplement dose adjustment
Visit 1 (Baseline)	> 9.5 mg/dL and < 500 mg supplemental oral calcium and no calcitriol	Start at 25 µg	Receive no supplemental calcitriol and oral calcium
	> 9.5 mg/dL on any dose of supplemental calcitriol or ≥ 500 mg oral calcium	Start at 50 µg	Stop supplemental calcitriol and oral calcium
	≤ 9.5 mg/dL on any dose of supplemental calcitriol or oral calcium	Start at 50 µg	Maintain supplemental calcitriol and oral calcium
Interim Safety Check: * 3-5 days post Visit 1  AND  * after significant change in supplements  *or after any adjustment in rhPTH[1-84] dose *or if clinically indicated	< 8.0 mg/dL	Maintain	Increase calcitriol dose or oral calcium dose as required*
	8.0 - 9.0 mg/dL	Maintain	No change in calcitriol dose; no change in oral calcium dose
	9.1 - 10.5 mg/dL	Maintain	Reduce calcitriol dose by up to 50%; if no longer receiving calcitriol then reduce oral calcium dose by up to 50% *
	10.6 - 11.9 mg/dL	Maintain	Reduce by up to 50% or eliminate calcitriol dose and/or oral calcium dose *
	> 11.9 mg/dL	Stop Study Drug until serum calcium is in the normal range on at least daily retesting	STOP calcitriol AND oral calcium dosing until serum calcium is in the normal range on at least daily retesting

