3.1. General Description

This study is a long-term, open-label study using rhPTH[1-84] for the treatment of adults with hypoparathyroidism. Subjects can enroll if they either previously completed the NPSP558 RELAY study (PAR-C10-007) (8 weeks of active therapy) and/or completed the REPLACE study (CL1-11-040) (Visit 18).

The goal of this study is to optimize rhPTH[1-84] dosing while reducing calcitriol and oral calcium (carbonate or citrate) supplementation to as low as safely possible and maintaining total serum calcium levels. Dose adjustments to rhPTH[1-84] and to the calcium/calcitriol supplements and safety monitoring of calcium levels are explained in protocol Appendix 2, rhPTH[1-84] and Supplement Titration Guideline.

- The starting dose of rhPTH[1-84] for this study will be 25 or 50 µg SC once daily (QD)
- Subjects may have their rhPTH[1-84] dose adjusted by the investigator at any time during the study, with the goal of achieving or maintaining total serum calcium levels in the range of 8.0 to 9.0 mg/dL.
- If **ANY** predose (trough) total serum calcium is >11.9 mg/dL study drug will be stopped.
- Subjects will have blood draws to assess total serum calcium levels (which may be performed locally) 3 to 5 days after **ANY** dose adjustment of rhPTH[1-84], after any significant change in doses of calcium and/or calcitriol supplements, or at any other time at the discretion of the investigator.
- Study visits during the first 12 months of the study will be conducted at Weeks 1 (baseline), 4, 8, and then every 8 weeks thereafter up to Week 48 (Visit 8). The Week 52 visit (Visit 9) is scheduled 4 weeks later.
- At any time following the Week 16 (Visit 4), subjects who are on a stable dose of rhPTH[1-84] and have a 24-hour urine calcium >300 mg (males) and >250 mg (females) may be treated for hypercalciuria with calcium-sparing diuretics, if this therapy had not been introduced prior to the study.
- At the end of Week 52, subjects will be invited to extend their study drug regimen until January 2018 or after the completion of the last patient's Month 72 visit, whichever comes last..
- During this time, subjects will return to the clinic for interim visits every 2 months (Months 14, 16, 18, etc).

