6.8.2. Clinical Laboratory Evaluation

All laboratory parameters will be collected and processed via a central laboratory, with exception of all urine pregnancy tests and total serum calcium levels which will be done at investigator's local laboratories. Standard international (SI) units will be used for data presentation. Only scheduled lab parameters will be included in the lab summaries. All lab data will be included in the listings.

Quantitative results will be summarized for hematology, serum chemistry, thyroid function tests (levothyroxine and thyroid-stimulating hormone), creatinine clearance, urinary chemistries (24-hour urine calcium, phosphate, and sodium excretion), and selected urinalysis parameters (pH, specific gravity, and urobilinogen) by visit. Both actual values and change from baseline will be summarized. Additionally, shift tables will be presented, summarizing cross tabulations of low,

normal, and high based on the parameter normal range, from baseline to each post-baseline visit and EOT. Percentages for shift tables will be based on the number of subjects with both baseline and post-baseline values at each visit.

Categorical urinalysis findings and urine pregnancy results will be presented in appendix data listings only.

Estimated creatinine clearance rate will be re-calculated based on the Cockcroft-Gault (C-G) equation:

$$\text{CLcr (mL/min)} = [140 - \text{age (years)}] \times \text{weight (kg)} \{ \times 0.85 \text{ for female subjects} \} / (72 \times \text{serum creatinine (mg/dL)}),$$

Estimated creatinine clearance rate will be summarized by stages as defined in Table 5.

Table 6.1 Definition of the Stages of Clcr3

Stage	Description	CLcr (mL/min)
1	Control (normal) Glomerular filtration rate (GFR)	≥ 90
2	Mild decrease in GFR	60-89
3	Moderate decrease in GFR	30-59
4	Severe decrease in GFR	15-29
5	End Stage Renal Disease (ESRD)	<15 not on dialysis
		Requiring dialysis

The number and percentage of subjects with post-baseline results qualifying as markedly abnormal will be summarized by parameter. A listing of all values for the parameter which qualifies as markedly abnormal will be provided. Markedly abnormal laboratory criteria are defined in Table 6.

Table 6.2 Markedly Abnormal Laboratory Criteria⁴

Lab parameter	Unit	Lower Limit	Upper Limit
Chemistry			
Albumin	g/L	≤20	≥90
Alkaline Phosphatase	U/L	NA	>2*ULN
ALT	U/L	NA	>3*ULN
Amylase	U/L	≤15	≥350
AST	U/L	NA	>3*ULN
Bilirubin	μmol/L	NA	>2*ULN
BUN	mmol/L	NA	≥10.7

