Calcium (total)	mmol/L	≤2.1	≥3.0
Chloride	mmol/L	≤80	≥125
Cholesterol (total)	mmol/L	NA	≥12.9
Creatinine	μmol/L	NA	≥177
Creatinine clearance	ml/min	≤60	NA

Glucose	mmol/L	<=1.7	>=13.9
Gamma glutamyl transferase	U/L	NA	>=100
Phosphate	mmol/L	NA	>=2
Potassium	mmol/L	<=2.5	>=6.5
Sodium	mmol/L	<=120	>=165
Triglycerides	mmol/L	NA	>=5.6
Uric acid	μmol/L	NA	>=624 (males) >=505 (females)
Hematology			
Hematocrit	L/L	<=0.37 (males) <=0.32 (females)	>0.54 (males) NA (females)
Hemoglobin	g/L	<=115 (males) <=95 (females)	NA
Platelets	10 ⁹ /L	<=75	>=700
RBC count	10 ¹² /L	<=2.5 (males) <=2.0 (females)	NA
WBC count	10 ⁹ /L	<=2.8	>=16.0
Basophils	L/L	NA	>=0.15
Eosinophils	L/L	NA	>=0.10
Lymphocytes	L/L	NA	>=0.80
Monocytes	L/L	NA	>=0.40
Neutrophils	L/L	<=0.15	NA
24-Hour urine			
Urine calcium	mg	NA	>300 for men >250 for women

NA=Not Applicable; ULN = Upper Limit of Normal

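### The SAP's markedly abnormal low limit for serum calcium (2.1 mmol/L, 8.42 mg/dL) lies inside the 8.0 to 9.0 mg/dL treatment target, so on-target values are counted as safety abnormalities

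*SAP*

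**What the plan says.** SAP 6.8.2 summarizes, by parameter, the number and percentage of subjects with any post-baseline result that meets the criteria in Table 6.2. For total calcium the row is "Calcium (total) mmol/L ≤2.1 ≥3.0". No mg/dL equivalent or derivation is given; the table is referenced to central-laboratory data on file from April 2010.

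The treatment target is stated in both documents. Protocol 3.1 allows rhPTH[1-84] dose changes "with the goal of achieving or maintaining total serum calcium levels in the range of 8.0 to 9.0 mg/dL", and adds: "Once a subject achieves a stable serum calcium (target: between 8.0 and 9.0 mg/dL"). SAP 3.1 repeats the aim of "achieving or maintaining total serum calcium levels in the range of 8.0 to 9.0 mg/dL". In the Appendix 2 titration tables, a value of 8.0 to 9.0 mg/dL leads to no change in study drug or supplements. The hypocalcemia paragraph of Appendix 2 begins "If the total serum calcium level falls below 8.0 mg/dL", with the subject's baseline as the reference for anyone who entered below 8.0. Protocol 1.1 gives the usual range: "Normal total serum calcium levels (generally 8.4 to 10.2 mg/dL").

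On which results are counted, SAP 6.8.2 says "Only scheduled lab parameters will be included in the lab summaries", and then "All lab data will be included in the listings".

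**The concern.** The limit and the target are in different units, which hides the overlap. After conversion, a subject held where the protocol wants them can be counted as having a marked safety abnormality. Both figures refer to total calcium, so albumin correction does not explain the difference.

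Long-term safety is the primary objective, the study is open-label with no control group, and no formal tests are planned. Descriptive counts carry the safety conclusions, and no comparator shows how many flags arise from on-target values alone. A reader of the finished table could not tell hypocalcemia from successful titration.

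The scheduled-only rule raises a smaller question. Calcium must be checked 3 to 5 days after any rhPTH[1-84] dose change or significant supplement change. Many of those checks are unscheduled and may be local, so they would not enter this count.

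**Working it through.** **Inputs.** Limits 2.1 and 3.0 mmol/L (SAP Table 6.2); target 8.0 to 9.0 mg/dL (Protocol 3.1, SAP 3.1); lower limit of normal 8.4 mg/dL (Protocol 1.1); stopping threshold above 11.9 mg/dL (Protocol 3.1, Appendix 2). Atomic masses are calcium 40.078 and phosphorus 30.974, so mg/dL = mmol/L × 4.0078 for calcium.

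**Check of the conversion.** The protocol equates a calcium phosphate product of 55 mg²/dL² with 4.4 mmol²/L². Recomputed: 55 × (10/40.078) × (10/30.974) = 4.43, which agrees.

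**Low limit against target.**
- 2.1 × 4.0078 = 8.42 mg/dL.
- 8.0/4.0078 = 1.996 and 9.0/4.0078 = 2.246, so the target is 2.00 to 2.25 mmol/L.
- Share of the band flagged: (8.416 − 8.0)/(9.0 − 8.0) = 0.42.
- 8.4/4.0078 = 2.096, which is below 2.1. The protocol's lower limit of normal is itself flagged.

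**Illustration of size.** The distribution is my assumption: normal values, mean 8.5 or 8.75 mg/dL, SD 0.25 to 0.4. For one value, P(flag) = Φ((8.416 − mean)/SD). For example, (8.416 − 8.5)/0.25 = −0.334 gives 36.9%, and (8.416 − 8.5)/0.4 = −0.209 gives 41.7%. Below 8.0 the same means and SDs give z = −2 and −1.25, that is 2.3% and 10.6%.

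For a subject with eight scheduled visits (Weeks 4, 8, 16, 24, 32, 40, 48 and 52) and common within-subject correlation ρ, P(at least one flag) = 1 − ∫[1 − Φ((z − √ρ·u)/√(1 − ρ))]⁸ φ(u) du. With ρ = 0 this is 1 − (1 − p)⁸.

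| Mean, SD (mg/dL) | Single value ≤8.42 | Single value <8.0 | Subjects ≤8.42, ρ = 0 | ρ = 0.5 | ρ = 0.8 | Subjects <8.0, ρ = 0 | ρ = 0.8 |
|---|---|---|---|---|---|---|---|
| 8.5, 0.25 | 37% | 2% | 98% | 79% | 63% | 17% | 7% |
| 8.5, 0.4 | 42% | 11% | 99% | 83% | 68% | 59% | 26% |
| 8.75, 0.25 | 9% | 0.1% | 53% | 34% | 23% | 1% | 1% |
| 8.75, 0.4 | 20% | 3% | 84% | 58% | 42% | 22% | 9% |

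In every row the count at 8.42 mg/dL is well above the count at 8.0 mg/dL. The difference is made up of subjects whose flagged values were all at 8.0 mg/dL or above.

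**High limit.** 3.0 × 4.0078 = 12.02 mg/dL, against the stopping threshold of 11.9 mg/dL (2.97 mmol/L). The gap is 0.12 mg/dL.

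**Scheduled-only rule.** The Week 1 local calcium is in the schedule table, so the clear omission is the unscheduled checks. SAP 6.8.2 also exempts total serum calcium from the central laboratory without qualification, while Protocol 6.2.3 exempts only baseline and interim samples. Which calcium feeds the table is therefore not fully settled.

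**The case against.** The limit is a generic laboratory criterion, close to the stated lower limit of normal, and no figure in the SAP is miscalculated. Clinical hypocalcemia is a separate endpoint based on adverse events. SAP 6.8.1 counts subjects and episodes for the overall trial, and shift tables and by-visit means remain. All of this is fair, and it limits the damage to one row of one descriptive table. It does not remove the overlap. A limit at the lower edge of normal is hard to call marked, and less so in a study that deliberately aims partly below that edge.

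Three stronger readings are tempting, and the documents do not support them.

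- A reader might infer that nearly every subject will be flagged, so that the count carries no information. That needs independent visits and a mean near 8.5 mg/dL. With ρ = 0.8 the first-year figure falls to 63 to 68%, and with mean 8.75 to between 23% and 42%.
- A reader might infer that extreme interim values disappear from the report. They do not: all results are listed, laboratory values judged clinically significant must be reported as adverse events, and such values may enter the episode counts. They are missing from this summary only.
- A reader might infer that the upper limit is wrong as well. A gap of 0.12 mg/dL is trivial, and nothing requires a reporting limit to equal a stopping threshold.

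**Conclusion.** The concern holds for the low limit. Applied exactly as written, SAP Table 6.2 counts on-target calcium values as markedly abnormal over about 42% of the target band. That finding needs only a unit conversion. The share of subjects affected rests on an assumed calcium distribution and correlation: about 63 to 99% in the first year with mean 8.5 mg/dL (7 to 59% below 8.0), and about 23 to 84% with mean 8.75.

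The omission of unscheduled checks is secondary, because those results are reported elsewhere. The study is descriptive and the other safety summaries are unaffected, so this should be fixed but does not undermine the safety analysis as a whole.

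**What to change.** These changes are to reporting only and leave patient management as it is.

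1. Reconcile the low calcium limit in Table 6.2 with the 8.0 to 9.0 mg/dL target so that on-target values are not counted. One way is to report values below the protocol's own 8.0 mg/dL line. State the limit in mg/dL or as 1.996 mmol/L: a value of exactly 8.0 mg/dL converts to 1.996, and a rounded limit of <2.00 mmol/L would flag it.
2. Do not add a tier at 7.5 mg/dL. In these documents that figure is only an efficacy floor, which Amendment 6 removed from the protocol as a carryover from REPLACE.
3. Beside the scheduled count, add a separate any-time count of subjects with low or high calcium that includes unscheduled and local results, marked as such. State which laboratory's calcium feeds each count.
4. Aligning the upper limit with 11.9 mg/dL is optional.

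The cost is one table row, a sentence or two and a little reprogramming. In the any-time count, subjects with more dose changes are tested more often and have more chances to be flagged, and local reference ranges differ. For that reason it should stand beside the scheduled count and not be pooled with it.

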6.8.3. ECG Evaluations

The number and percentage of subjects with each type of ECG finding (Normal/Abnormal, Not Clinically Significant/Abnormal, and Clinically Significant) will be presented by visit.

Actual value and change from baseline for each ECG parameters (HR, PR, QRS, QT, QTcB, QTcF) will be presented by visit.

Potentially clinically significant QTc finding criteria are defined in Table 7. The number and percentage of subjects with post-baseline results qualifying as potentially significant will be summarized by parameter. A listing will present all values for a subject and parameter for cases where at least one value for that parameter was potentially significant.

Table 6.3 Potentially Clinically Significant Post-Baseline ECG^{5,6}

ECG Parameter	Potentially Clinical Significant Criterion
QTcB	≥ 500 ms
QTcF	≥ 500 ms
QTcB	An increase from Baseline of ≥ 60 ms or ≥ 30 ms
QTcF	An increase from Baseline of ≥ 60 ms or ≥ 30 ms

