#### **6.2.5 Electrocardiograms**

A 12-lead ECG will be done at baseline, Week 52, and at the End of Treatment visit. Baseline and Week 52 ECGs (and early termination visits occurring in the first year) will be done at the study center on the same model unit. The end of treatment ECG may be done locally. Recorded data will include general findings, ventricular rate (bpm) and P-R, QRS, and QTc intervals (seconds). Any ECG abnormalities, as determined by the investigator, at screening will be recorded as medical history. Any clinically significant adverse change from the status at the screening visit and noted to be clinically significant by the investigator should be captured as an

AE. All ECGs conducted during the first year of the study will be assessed by a central reader and this assessment will be used as the primary data readout for the study. However, investigators are also responsible for providing their own interpretation of the ECG, and this will be captured on the ECG print out. Two copies of the ECG tracings should be retained in the subject source record. The local, end of treatment ECG will not be sent to the central reader, unless necessary in order to confirm an ambiguous result or serious abnormality.

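### The only ECG scheduled after Week 52 is read locally, and SAP 6.8.3 does not separate it from the centrally read ECGs in the QTc outlier count or in the End of Treatment row

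*SAP*

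**What the plan says.** Protocol 6.2.5 sets the schedule: "A 12-lead ECG will be done at baseline, Week 52, and at the End of Treatment visit". No ECG appears in the extension tables between Week 52 and EOT, although Protocol 3.2 allows up to 80 months of treatment.

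For the first year, Protocol 6.2.5 says that the baseline, Week 52 and first-year early-termination ECGs "will be done at the study center on the same model unit", and that "All ECGs conducted during the first year of the study will be assessed by a central reader". It makes that assessment the study's primary readout.

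For the end of the study the same section says: "The end of treatment ECG may be done locally". Footnote g of Protocol Table 6-3, repeated in SAP Table 4.3, states that this ECG is read locally. Central review is the exception, reserved for an unclear or seriously abnormal tracing: "The local, end of treatment ECG will not be sent to the central reader, unless necessary in order to confirm an ambiguous result or serious" …

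The ECG fields listed in Protocol 6.2.5 are general findings, ventricular rate, PR, QRS and a QTc with no named correction. Uncorrected QT is not in the list.

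SAP 6.8.3 asks for this: "Actual value and change from baseline for each ECG parameters (HR, PR, QRS, QT, QTcB, QTcF) will be presented by visit". It then counts, by parameter, subjects whose results after baseline meet the QTcB or QTcF criteria in Table 6.3: a value of at least 500 ms, or an increase of at least 60 or 30 ms. Reader and unit are not mentioned.

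**The concern.** The primary objective is long-term safety, and all scheduled QTc evidence beyond one year rests on one ECG. That ECG is obtained by a different reading process from the ECGs it is compared with and counted alongside. If local reading or a local unit shifts QTc, the shift looks like a change on treatment; a shift the other way could hide one. A reader of the clinical study report could not tell which had happened, because nothing in the planned tables shows which reader produced a value.

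The listed ECG fields add to the difficulty. The SAP needs QT, QTcB and QTcF at each visit. A local printout with a single unlabelled QTc supplies none of them.

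**Working it through.** The plan contains no QTc assumption or precision figure to reproduce. The check sets the passages side by side and then illustrates scale.

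**Step 1. How each ECG is obtained**

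| ECG | Unit | Reader | Source |
|---|---|---|---|
| RACE Visit 1 | same model, study center | central | Protocol 6.2.5 |
| Week 52 | same model, study center | central | Protocol 6.2.5 |
| Early termination, Year 1 | same model, study center | central | Protocol 6.2.5 |
| EOT after Year 1 | local permitted | local; central only for ambiguous or serious results | Protocol 6.2.5, Table 6-3; SAP Table 4.3 |
| REPLACE or RELAY baseline | not stated | not stated | SAP 5.3.2 |

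**Step 2. Where each value goes**

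- Change from baseline is tabulated by visit, so Week 52 and EOT are separate rows. The Week 52 row is centrally read.
- SAP 5.1 defines EOT as the last value obtained between first dose and one day after last dose. Year 1 terminators therefore put central reads into the EOT row. So does a subject whose final ECG falls outside that period and whose Week 52 value is used instead. Other subjects contribute local reads.
- The Table 6.3 counts run over all results after baseline, so central Week 52 and local EOT values can each place a subject in the same count.
- For prior completers, SAP 5.3.2 takes the baseline from REPLACE or RELAY. These documents do not give the reader or unit for those ECGs. Even the Week 52 change is therefore not shown to be a same-method comparison.

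**Step 3. What a method shift would do (illustration)**

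From the documents: about 50 subjects (Protocol 4.1) and the 30 and 60 ms limits. Assumed: normally distributed changes, true mean change 0, SD s of 15 to 25 ms, method shift b of -10 to +10 ms, and all 50 EOT reads local.

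Expected subjects with an increase of at least 30 ms = 50 × [1 − Φ((30 − b)/s)]:

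| s (ms) | b = -10 | b = 0 | b = +10 |
|---|---|---|---|
| 15 | 0.2 | 1.1 | 4.6 |
| 20 | 1.1 | 3.3 | 7.9 |
| 25 | 2.7 | 5.8 | 10.6 |

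For example, s = 20 and b = +10 gives 1 − Φ(1.0) = 0.1587, and 50 × 0.1587 = 7.9. At the 60 ms limit the same case moves only from 0.07 to 0.31 subjects.

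The 95% half-width of a mean change is 1.96 × s/√50, which is 4.2, 5.5 and 6.9 ms for s of 15, 20 and 25. If 60% to 100% of the EOT row were local reads (assumed), a 10 ms shift would move the row mean by 0.6 × 10 = 6 ms to 1.0 × 10 = 10 ms. That is about the size of the sampling error or larger.

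**Step 4. The correction formula**

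With RR = 60/heart rate, QTcB = QT/RR^(1/2) and QTcF = QT/RR^(1/3). At an assumed QT of 380 ms:

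| Heart rate (bpm) | QTcB | QTcF | Difference (ms) |
|---|---|---|---|
| 70 | 410 | 400 | 10 |
| 80 | 439 | 418 | 21 |
| 90 | 465 | 435 | 30 |

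These differences enter the results only if an unlabelled QTc is filed under the wrong parameter.

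**The case against.** Several points on the other side are sound.

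- A reader might infer that the SAP merges central and local reads throughout its change-from-baseline table. It does not: that table is by visit, with EOT in addition to the scheduled visits. The mixing is in the outlier count and inside the EOT row. SAP 6.8.3 also lists all values for each flagged subject and parameter, though without requiring the reader to be shown.
- A change of machine is permitted, not required.
- A reader might infer that a switch of formula alone takes subjects past the 30 ms limit. QTcB and QTcF are analysed separately, each against its own baseline, so this needs a misfiled QTc and a heart rate near 90 bpm. Missing data is at least as likely a result. CRF instructions are kept in other documents, so QT may be captured even though Protocol 6.2.5 does not list it.
- The primary-readout sentence could mean that the tables use central reads only. On that reading almost no QTc data would remain after Year 1, and SAP 6.8.3 does not adopt it.
- Protocol 6.2.5 describes central review of selected EOT tracings as confirmation. It does not say that the central value replaces the local one, so biased outlier counts from selective re-reading are possible but not shown.
- The study is uncontrolled and descriptive. One reader throughout would still not isolate a drug effect.

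The last point limits what any QTc result here can claim. It does not justify adding an avoidable change of method that the tables do not show.

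**Conclusion.** The point holds. Followed as written, the plan gives a long-term QTc result that mixes reading methods: the outlier count combines central and local reads, and the EOT row can do the same. The change after Week 52 cannot be separated from a change of reader, and possibly of machine.

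The documents do not allow the size or direction of any bias to be stated. The figures above depend on assumed shifts and SDs. They show only that a 10 ms method shift would matter for the 30 ms count and the mean, and little for the 60 ms count. A formula switch is possible but not shown.

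The point does not support dropping EOT ECGs from the criteria for increase, since they are the only scheduled QTc screen beyond Year 1. It should be corrected in the SAP; it does not undermine the study.

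**What to change.** In SAP 6.8.3:

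1. Report QTc change from baseline, and the counts for at least 500 ms and for increases of at least 30 and 60 ms, separately for centrally and locally read ECGs. Carry a reader flag in tables and listings.
2. Keep local EOT results against all the criteria, labelled as a separate safety screen. State how the primary-readout sentence in Protocol 6.2.5 applies to these tables, and which value is used when an EOT tracing has also been read centrally.
3. Derive QTcB and QTcF at every visit from QT and heart rate by the stated formulas. Do not use an unlabelled printed QTc.
4. State which ECG is the baseline: REPLACE or RELAY under SAP 5.3.2, or RACE Visit 1. Because Visit 1 is the one these documents show as same-unit and centrally read, also present the Week 52 change from Visit 1.

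The cost is a few extra table rows, and entry of QT from the tracings that Protocol 6.2.5 asks sites to retain wherever it was not captured. That entry is new data collection. The other cost is giving up any claim of a within-method QTc change beyond Week 52. Central reading of all retained EOT tracings would remove the reader difference at greater expense, but not a difference in unit.
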